## **9. SAFETY AND TOLERABILITY**

[Appendix A](#) provides a list of data displays. Sample data displays are included in a separate document.

### **9.1. General Considerations**

Summary tables may be replaced with listings when appropriate. For instance, an AE frequency table may be replaced with a listing if it only contains a few unique preferred terms reported on relatively few participants.

Unless otherwise stated, table summaries will be limited to AEs occurring within 30 days after the last application of ruxolitinib cream.

### **9.2. Adverse Events**

#### **9.2.1. Adverse Event Definitions**

A TEAE is any AE either reported for the first time or worsening of a pre-existing event after the first application of study drug until 30 days after the last application of study drug. Analysis of AEs (as discussed below) will be limited to TEAEs, but data listings will include all AEs regardless of their timing in relation to study application.

Adverse events will be tabulated by MedDRA PT and SOC. Severity of AEs will be graded using the NCI CTCAE v5. The CTCAE reporting guidelines and grading details are available on the Cancer Therapy Evaluation Program website.

The subset of AEs considered by the investigator to be related to study drug will be considered to be treatment-related AEs. If the investigator does not specify the relationship of the AE to study drug, the AE will be considered to be treatment-related. The incidence of AEs and treatment-related AEs will be tabulated. In addition, serious TEAEs will also be tabulated.

Any missing onset date, causality, or severity must be queried for resolution. Unresolved missing causality and severity will be handled according to the following rules:

- An unresolved missing causality will be considered treatment-related.
- An unresolved missing severity will be identified as an unknown severity.

For purposes of analysis, all AEs will be considered TEAEs unless the AE can unequivocally be defined as not treatment-emergent.

An application site reaction is an AE that occurs solely at one or more sites of ruxolitinib cream application and could be related to application of ruxolitinib cream. A summary of ASRs will be provided.

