8.2.3. Investigator's Global Assessment

Investigator's Global Assessment is an overall eczema severity rating on a 0 to 4 scale that will be assessed for the whole body (total IGA) and for the face only (facial IGA) during site visits as outlined in the SoA (see Table 3 [CT period] and Table 4 [LTS period]). The area "Face" is defined as including the area on the forehead to the original hairline, on the cheek to the jawline vertically to the jawline and laterally from the corner of the mouth to the tragus. The area "Face" will not include the surface area of the lips, scalp, ears, or neck but will include the nose and eyelids. The severity strata for the IGA are shown in Table 8.

Table 8: Investigator's Global Assessment

Grade	Severity	Status
0	Clear	No erythema or induration/papulation, no oozing/crusting; there may be minor residual discoloration
1	Almost clear	There may be trace faint pink erythema, with almost no induration/papulation, and no oozing/crusting
2	Mild	There may be faint pink erythema, with mild induration/papulation and no oozing/crusting
3	Moderate	There may be pink-red erythema with moderate induration/papulation and there may be some oozing/crusting
4	Severe	There may be deep or bright red erythema with severe induration/papulation and with oozing/crusting

Source: FDA 2012.

Participants must have a total IGA score of 2 or 3 at the screening and baseline visits to enroll in the study; there is no limitation for total or facial IGA score at Week 8 (baseline for the LTS period) to enter the LTS period.

During the LTS period, including Week 8 (baseline for the LTS period), total IGA will be evaluated by the investigator to determine whether the participant requires continuation of treatment or should (re)enter an observation/no treatment cycle. If the total IGA score is ≥ 1, the participant will start or continue active treatment with ruxolitinib cream 1.5% BID. If the total IGA score is 0 (clear), the participant will (re)enter an observation/no treatment cycle.

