10.4. Statistical Analyses

10.4.1. Primary Analysis

A TEAE is any AE either reported for the first time or worsening of a pre-existing event after first application of study cream and up to 30 days after the last application of study cream. Analysis of AEs will be limited to TEAEs, but data listings will include all AEs regardless of their timing in relation to study cream application. Treatment-emergent AEs will be tabulated by the MedDRA preferred term and system organ class. Severity of AEs will be based on CTCAE v5.0 using Grades 1 through 5.

The subset of AEs considered by the investigator to have a relationship to study cream will be considered to be treatment-related AEs. If the investigator does not specify the relationship of the AE to study cream, then the AE will be considered treatment-related. The incidence of TEAEs, treatment-related TEAEs, serious TEAEs, Grade 3 or higher TEAEs, and TEAEs leading to

study cream interruption or study discontinuation will also be tabulated. A summary of primary endpoint analyses is provided in Table 12.

Table 12: Summary of Primary Endpoint Analyses

Endpoint	Population	Treatment	Population-Level Summary Metric
Incidence of TEAEs, treatment-related TEAEs, serious TEAEs, Grade 3 or higher TEAEs	FAS	Ruxolitinib 1.5% BID cream	Rate of TEAEs
Incidence of TEAEs leading to study cream interruption or study discontinuation	FAS	Ruxolitinib 1.5% BID cream	Rate of TEAEs
Incidence of TEAEs summarized by Grades of AE	FAS	Ruxolitinib 1.5% BID cream	Rates of TEAEs

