**Figure 1: Study Design Schema**

a At Week 8, to qualify for the LTS period, an IGA score of 0 to 4 and %BSA affected by AD of 0% to  $\leq 20\%$  will be required.

b Treatment is ceased 3 days after clearing of AD lesions. Treatment is restarted if AD lesions recur. There is no limit to the number of treatment cycles during the 44-week LTS period.

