3.2.1.1.2	Overall Summary of Treatment-Emergent Adverse Events in the CT Period by Sex	FAS
3.2.1.1.3	Overall Summary of Treatment-Emergent Adverse Events in the CT Period by Race	FAS
3.2.1.1.4	Overall Summary of Treatment-Emergent Adverse Events in the CT Period by Ethnicity	FAS
3.2.1.2.1	Overall Summary of Treatment-Emergent Adverse Events in the LTS Period	LTS-EV
3.2.1.2.2	Overall Summary of Treatment-Emergent Adverse Events in the LTS Period by Sex	LTS-EV
3.2.1.2.3	Overall Summary of Treatment-Emergent Adverse Events in the LTS Period by Race	LTS-EV
3.2.1.2.4	Overall Summary of Treatment-Emergent Adverse Events in the LTS Period by Ethnicity	LTS-EV
3.2.1.3.1	Overall Summary of Treatment-Emergent Adverse Events From Baseline to Week 52	FAS
3.2.1.3.2	Overall Summary of Treatment-Emergent Adverse Events From Baseline to Week 52 by Sex	FAS
3.2.1.3.3	Overall Summary of Treatment-Emergent Adverse Events From Baseline to Week 52 by Race	FAS
3.2.1.3.4	Overall Summary of Treatment-Emergent Adverse Events From Baseline to Week 52 by Ethnicity	FAS
3.2.2.1	Summary of Treatment-Emergent Adverse Events by MedDRA System Organ Class and Preferred Term in the CT Period	FAS
3.2.2.2	Summary of Treatment-Emergent Adverse Events by MedDRA System Organ Class and Preferred Term in the LTS Period	LTS-EV
3.2.2.3	Summary of Treatment-Emergent Adverse Events by MedDRA System Organ Class and Preferred Term From Baseline to Week 52	FAS
3.2.3.1.1	Summary of Treatment-Emergent Adverse Events by MedDRA Preferred Term in Decreasing Order of Frequency in the CT Period	FAS
3.2.3.1.2	Summary of Treatment-Emergent Adverse Events by MedDRA Preferred Term in Decreasing Order of Frequency in the CT Period by Sex	FAS
3.2.3.1.3	Summary of Treatment-Emergent Adverse Events by MedDRA Preferred Term in Decreasing Order of Frequency in the CT Period by Race	FAS

Table No.	Title	Population
3.2.3.1.4	Summary of Treatment-Emergent Adverse Events by MedDRA Preferred Term in Decreasing Order of Frequency in the CT Period by Ethnicity	FAS
3.2.3.2.1	Summary of Treatment-Emergent Adverse Events by MedDRA Preferred Term in Decreasing Order of Frequency in the LTS Period	LTS-EV
3.2.3.2.2	Summary of Treatment-Emergent Adverse Events by MedDRA Preferred Term in Decreasing Order of Frequency in the LTS Period by Sex	LTS-EV
3.2.3.2.3	Summary of Treatment-Emergent Adverse Events by MedDRA Preferred Term in Decreasing Order of Frequency in the LTS Period by Race	LTS-EV

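### The TEAE window closes 30 days after the last application in the study, so an AE starting more than 30 days into a drug-free cycle is tabulated only if the participant is re-treated later.

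*SAP*

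**What the plan says.** Protocol 10.4.1 and SAP 9.2.1 give the same rule. The protocol counts events "after first application of study cream and up to 30 days after the last application of study cream"; the SAP counts them "after the first application of study drug until 30 days after the last application of study drug". SAP 9.1 adds that, unless otherwise stated, "table summaries will be limited to AEs occurring within 30 days after the last application of ruxolitinib cream". Neither SAP 9.2.2 nor the table list in SAP Appendix A states otherwise for any AE table.

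Two further sentences in SAP 9.2.1 matter. Listings are wider than tables: "data listings will include all AEs regardless of their timing in relation to study application". There is also a default: "all AEs will be considered TEAEs unless the AE can unequivocally be defined as not treatment-emergent".

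The LTS period is intermittent. Protocol 8.2.3 says: "If the total IGA score is 0 (clear), the participant will (re)enter an observation/no treatment cycle". Treatment restarts on recurrence, and the footnote to SAP Figure 1 says: "There is no limit to the number of treatment cycles during the 44-week LTS period". Protocol Table 4 schedules AE assessment at Weeks 12, 20, 28, 36, 44 and 52, whether or not the participant is on treatment at the time.

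SAP 5.3.1 uses the FAS for whole-study safety. Appendix A plans, among others, Table 3.2.1.3.1, "Overall Summary of Treatment-Emergent Adverse Events From Baseline to Week 52".

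**The concern.** A single window ending 30 days after the last application suits continuous dosing. Here a participant can clear, stop, remain under observation for months, and either relapse or not. Beyond the first 30 drug-free days, whether an event enters the tables depends on something that happens after it, namely re-treatment.

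The tabulated proportion is then hard to interpret. It is not an on-treatment incidence, because months of drug-free time count for anyone later re-treated. It is not an on-study incidence either, because the same kind of time does not count for those who stay clear. Both groups share one denominator under a title that refers to the whole year.

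The stake is the primary endpoint of a study whose stated purpose (Protocol 2.2) is additional long-term safety data in adolescents, and which is a post-marketing requirement. SAP 9.2.2 lists malignancies and thromboembolic events among the AEs of interest. With about 100 participants, one late event in or out of a table is visible.

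**Working it through.** **The plan's own figure.** Protocol 10.1 claims more than a 99% chance of seeing at least one AE of interest at a 5% rate with about 100 participants. 1 − 0.95^100 = 0.9941, so the claim reproduces. It presumes that all 100 are observed for the period to which the 5% refers.

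**The rule applied to two participants.** Both are clear at Week 8, last apply cream on Day 56, and have an AE on Day 100.
- Participant A relapses and re-applies on Day 200. The last application is now Day 200 or later, so the Day 100 event is a TEAE.
- Participant B never re-applies. The window closed on Day 56 + 30 = Day 86, so the Day 100 event is not a TEAE.

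An AE on Day 80 is a TEAE for both. The default that favours treatment-emergence does not help B, because a known onset on Day 100 is unequivocally outside the window.

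**Time outside the window for a participant never re-treated.** Conventions: Week w visit = Day 7w + 1; last application the day before that visit; window closes 30 days later; Week 52 = Day 365. Days outside = max(0, 365 − closing day).

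| Last application | Window closes | Days outside, to Week 52 |
|---|---|---|
| Day 56 (Week 8) | Day 86 | 279 |
| Day 140 (Week 20) | Day 170 | 195 |
| Day 196 (Week 28) | Day 226 | 139 |
| Day 252 (Week 36) | Day 282 | 83 |
| Day 308 (Week 44) | Day 338 | 27 |
| Day 336 (Week 48) | Day 366 | 0 |

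**Illustrative effect on the whole-study proportion.** The documents give neither the true incidence nor the share never re-treated. Assume a 52-week incidence of 60%, the same constant hazard on and off drug, and full follow-up.
- Hazard = −ln(0.4)/52 = 0.01762 per week.
- Tabulated incidence in those who stop for good at week t = 1 − exp(−0.01762 × (t + 30/7)). For t = 8, 20 and 32 this is 19.5%, 34.8% and 47.2%.
- With a share f stopping for good, the FAS figure = (1 − f) × 60% + f × that value.

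| Share f | t = 8 | t = 20 | t = 32 |
|---|---|---|---|
| 10% | 55.9% | 57.5% | 58.7% |
| 20% | 51.9% | 55.0% | 57.4% |
| 30% | 47.8% | 52.4% | 56.2% |

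The starting 60% is itself arbitrary. For f = 20% and t = 8, the same formula turns an assumed 40% into 34.3% and an assumed 80% into 70.3%.

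**Effect on detecting a 5% event.** Assume a constant hazard of −ln(0.95)/364 per day. A participant whose window closes on Day 86 has probability 1 − exp(−hazard × 86) = 0.0120 of a tabulated event. Detection = 1 − (1 − 0.0120)^(100f) × 0.95^(100(1 − f)). If the share f is clear from Week 8 and never re-treated, this gives 99.1%, 98.7% and 98.1% for f = 10%, 20% and 30%, against 99.4%.

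**The case against.** The strongest reply is that this is an ordinary treatment-emergent definition, agreed between protocol and SAP, and that events long after the last dose do not belong in it. The endpoint is called incidence of TEAEs, not 52-week incidence of all AEs. That would settle the matter if the rule excluded drug-free time consistently. It does not: it counts events months off drug in anyone who later restarts.

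Other parts of the reply stand and limit the point.
- A reader might infer that every AE in a drug-free cycle depends on later re-treatment. The first 30 days of each such cycle always count.
- A reader might infer that durable responders' AEs vanish from all tables. Their AEs on treatment, or within 30 days after it, stay in the FAS tables for the continuous treatment period and for Baseline to Week 52.
- A reader might infer that late malignancies or thromboembolic events are lost. They are not: SAP Appendix A plans listings of all AEs (2.7.1), serious AEs (2.7.3) and AEs of interest (2.7.9), and expedited SAE reporting under Protocol 9.4 does not depend on the TEAE flag. SAP 9.2.2 also allows a listing in place of a table when two or fewer participants are affected.
- Participants who discontinue study treatment have an early termination visit and a follow-up 30 to 37 days later, so little of their scheduled follow-up lies outside the window. Those mainly affected are participants who clear and stay clear under observation. Treatment resumes at the first sign of recurrence in a disease the protocol calls recurring, so 20% clear for good from Week 8 is a severe scenario.
- A participant with no LTS application is outside the LTS-evaluable population (SAP 5.3.3) and leaves both numerator and denominator of the LTS tables. For that participant the mismatch is confined to the FAS tables. One who applies cream in the LTS period and then clears for good is affected in the LTS tables too.

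**Conclusion.** The point holds in this form: for AEs starting more than 30 days into a drug-free cycle, inclusion in the tables depends on later re-treatment, and for participants never re-treated these AEs appear only in listings. The tabulated proportion is therefore neither a clean on-treatment nor an on-study incidence. This follows from the wording alone, reading the last application as the last in the study, which is the natural reading since no cycle-level definition is given.

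The time uncounted per affected participant runs from 279 days (last application Day 56) to 27 days (Week 44) and none (Week 48). The number of such participants is unknown. The range of 47.8% to 58.7% against 60% is illustrative; it rests on the assumed incidence, equal hazard on and off drug, and 10% to 30% never re-treated. The effect on the plan's detection claim is modest. The planned listings keep the late events visible individually, but they do not give the incidence that the primary endpoint asks for. The change is worth making before the tables are run because it costs little; the finding does not invalidate the TEAE tables.

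**What to change.** Keep the TEAE tables as planned.

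1. In SAP 9.1 and 9.2.1, state that the last application means the last in the study.
2. Add supplementary FAS on-study tables: overall summary, serious AEs and AEs of interest, with system organ class and preferred term. Count all AEs from first application to last study contact, whatever the date of the last application.
3. In those tables, flag each AE as starting within or beyond 30 days of the most recent application, using the cycle start and end dates that Protocol Table 4 already has sites record.
4. If on-cycle and off-cycle rates are to be compared, give person-time for each category; counts alone would not support a comparison.

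The cost is a few extra tables and one derived flag, from data already collected, with no change to study conduct. The downside is that off-drug events appear in the supplementary tables; the flag shows which they are.

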### 9.2.2. Adverse Event Summaries

An overall summary of AEs by treatment period will include the following:

- Number (%) of participants who had any TEAEs
- Number (%) of participants who had any ASRs
- Number (%) of participants who had any serious TEAEs
- Number (%) of participants who had any Grade 3 or higher TEAEs
- Number (%) of participants who had any treatment-related TEAEs
- Number (%) of participants who temporarily interrupted ruxolitinib cream because of TEAEs
- Number (%) of participants who permanently discontinued ruxolitinib cream because of TEAEs
- Number (%) of participants who had a fatal TEAE

Subgroup analysis (sex, race, ethnicity) for overall TEAEs will also be provided.

The following summaries will be produced by MedDRA term (if 2 or fewer participants appear in a table, a listing may be appropriate):

- Summary of TEAEs by MedDRA SOC and PT
- Summary of TEAEs by MedDRA PT in decreasing order of frequency
- Summary of ASRs by MedDRA PT in decreasing order of frequency
- Summary of Grade 3 or higher TEAEs by MedDRA SOC and PT
- Summary of Grade 3 or higher TEAEs by MedDRA PT in decreasing order of frequency
- Summary of serious TEAEs by MedDRA SOC and PT
- Summary of serious TEAEs by MedDRA PT in decreasing order of frequency
- Summary of treatment-related TEAEs by MedDRA SOC and PT
- Summary of treatment-related TEAEs by PT in decreasing order of frequency
- Summary of Grade 3 or higher treatment-related TEAEs by MedDRA SOC and PT
- Summary of treatment-related serious TEAEs by MedDRA SOC and PT
- Summary of TEAEs with a fatal outcome by MedDRA SOC and PT

- Summary of TEAEs leading to ruxolitinib cream dose interruption by MedDRA SOC and PT
- Summary of TEAEs leading to discontinuation of ruxolitinib cream by MedDRA SOC and PT

Subgroup analysis (sex, race, ethnicity) for TEAEs by MedDRA PT will also be provided.

Adverse events of interest will be summarized in the following categories:

- Cytopenias
  - Anemia
  - Thrombocytopenia
  - Neutropenia
- Herpes zoster
- Nonmelanoma skin neoplasms
- Liver function test elevations
- Malignancies
- Major Adverse Cardiovascular Events
- Venous and arterial thromboembolic events
- Thrombocytosis and elevated mean platelet volume

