4. STUDY DESIGN

4.1. Overall Design

This is a Phase 3, open-label, 1-year safety study of ruxolitinib cream in adolescents (ages ≥ 12 years to < 18 years) with AD whose disease is not adequately controlled with topical prescription therapies or when those therapies are not advisable (see study design schema in Figure 1). The study will be conducted at approximately 40 sites in North America and Europe.

Approximately 100 participants with a diagnosis of AD (as defined by the Hanifin and Rajka [1980] criteria) with a duration of disease of at least 2 years, a total IGA score of 2 or 3, and %BSA affected by AD of 3% to 20% (excluding the scalp) will be enrolled.

All participants will apply ruxolitinib cream at the FDA-approved strength (1.5%) BID using the same treatment paradigm as the INCB 18424-303 and -304 Phase 3 AD studies, namely starting with an 8-week CT period during which participants will treat all baseline AD lesions, regardless of whether or not the lesion(s) improve, followed by a 44-week LTS period during which participants will only treat active AD lesions.

Participants who complete the Week 8 assessments with no safety concerns and with %BSA affected by AD no greater than 20% will continue into the LTS period.

During the LTS period (ie, starting at the Week 8 visit), the treatment regimen will continue to be ruxolitinib 1.5% cream BID; however, participants will only treat active AD lesions. Participants will have the next study visit at Week 12, and then subsequent study visits will occur every 8 weeks until the end of the study (44 weeks total in the LTS period and 52 weeks total in the study). At those study visits, AD lesions will be evaluated by the investigator to confirm if the participant still requires continuation of therapy (total IGA score \geq 1) or can otherwise (re)enter the observation/no treatment cycle (total IGA score = 0). Refer to Section 6.1 for further details.

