4.2. Overall Study Duration

The study begins when the first participant signs the study ICF. The end of the study is defined as the date of the last visit of the last participant in the study or the date that the last participant has discontinued study cream and has completed applicable safety follow-up assessments or is lost to follow-up.

Participants will participate in the study for a duration of up to approximately 60 weeks: 28 days in the screening period, 8 weeks in the CT period, 44 weeks in the LTS period, and 30 days in the safety follow-up period (see Figure 1).

A participant is considered to have completed the study if they have completed all study visits, including the safety follow-up visit.

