### **5.3. Analysis Populations**

#### **5.3.1. Full Analysis Set**

The FAS will include all participants who applied ruxolitinib cream at least once.

The FAS will be used for the summary of demographics, baseline characteristics, participant disposition, analyses of all efficacy data, and safety for the CT period and for the whole study as well.

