### Tables

Table No.	Title	Population
Baseline and Demographics Characteristics		
1.1 Disposition		
1.1.1	Analysis Populations	FAS
1.1.2.1	Summary of Participant Disposition in the CT Period	FAS
1.1.2.2	Summary of Participant Disposition in the LTS Period	LTS-EV
1.1.3	Summary of Number of Participants Enrolled by Country and Site	FAS
1.1.4.1	Summary of Protocol Deviations for the CT Period	FAS
1.1.4.2	Summary of Protocol Deviations for the LTS Period	LTS-EV
1.2 Demography and Baseline Characteristics		
1.2	Summary of Demographics and Baseline Characteristics	FAS
1.3 Baseline Disease Characteristics		
1.3	Summary of Baseline Disease Characteristics	FAS
1.4 Prior Medication and Concomitant Medication		
1.4.1	Summary of Prior Medications	FAS
1.4.2	Summary of Prior Medications for Atopic Dermatitis	FAS
1.4.3.1	Summary of Concomitant Medications in the CT Period	FAS
1.4.3.2	Summary of Concomitant Medications in the LTS Period	LTS-EV
1.5+ Others		
1.5	Summary of General Medical History	FAS
Efficacy		
2.1 IGA		
2.1.1.1	Summary of Participants Achieving IGA-TS by Visit	FAS
2.1.1.2	Summary of Participants in Each Category of IGA Score by Visit	FAS
2.1.1.3	Summary of Participants Achieving an IGA score of 0 or 1 by Visit	FAS
2.1.1.4	Summary of Participants Achieving a Facial IGA score of 0 or 1 by Visit	FAS
2.2 EASI		
2.2.1	Summary of Participants Achieving EASI75 by Visit During the Treatment Period	FAS
2.2.2	Summary of EASI Score by Visit During the Treatment Period	FAS
2.3 Itch NRS Score		
2.3.1	Summary of Participants Achieving $\geq$ 4-Point Improvement in Itch NRS Score by Visit During the Treatment Period	FAS with baseline Itch NRS score $\geq$ 4
2.3.2	Summary of By-Visit Itch NRS Score	FAS
2.3.3	Summary of Participant Achieving $\geq$ 4-Point Improvement in Daily Itch NRS Score	FAS with baseline Itch NRS score $\geq$ 4
2.3.4	Summary of Daily Itch NRS Score	FAS

Table No.	Title	Population
2.4 BSA		
2.4.1	Summary and Analysis of Total %BSA Affected by AD	FAS
Safety		
3.1 Exposure		
3.1.1.1	Summary of Exposure in the CT Period	FAS
3.1.1.2	Summary of Exposure in the LTS Period	LTS-EV
3.1.1.3	Summary of Exposure from Baseline to Week 52	FAS
3.1.2	Summary of Study Drug Compliance in the CT Period	FAS
3.1.3	Summary of Study Drug Compliance in the LTS Period	LTS-EV
3.2 Adverse Events		
3.2.1.1.1	Overall Summary of Treatment-Emergent Adverse Events in the CT Period	FAS

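### Adverse events are planned as crude percentages with no person-time, so the 8-week and 44-week figures cannot be compared and the one-year figure is uncorrected for unequal follow-up

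*SAP*

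**What the plan says.** The trial has a single arm and a descriptive safety objective. Protocol 4.2 sets out "8 weeks in the CT period, 44 weeks in the LTS period", and Protocol 4.1 gives the totals as "44 weeks total in the LTS period and 52 weeks total in the study".

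SAP 9.2.2 states "An overall summary of AEs by treatment period will include the following", followed by items such as "Number (%) of participants who had any TEAEs". Appendix A then lists three versions of the overall table:

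- 3.2.1.1.1, "Overall Summary of Treatment-Emergent Adverse Events in the CT Period" (FAS)
- 3.2.1.2.1, "Overall Summary of Treatment-Emergent Adverse Events in the LTS Period" (LTS-EV)
- 3.2.1.3.1, "Overall Summary of Treatment-Emergent Adverse Events From Baseline to Week 52" (FAS)

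The same three-way layout runs through the later adverse event families, up to 3.2.16. SAP 5.3.1 assigns the FAS to "safety for the CT period and for the whole study as well". SAP 5.3.3 limits LTS-EV to participants with at least one application in the LTS period. SAP 9.2.1 closes the TEAE window 30 days after the last application.

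Exposure is summarised separately (SAP 6.4; Appendix A tables 3.1.1.1 to 3.1.1.3). Neither SAP 9.2 nor any title in Appendix A mentions events per person-time, time to first event, or incidence by interval within the LTS period.

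**The concern.** A crude percentage grows with the length of time over which events are counted. Setting an 8-week percentage beside a 44-week one invites a comparison that the numbers cannot support. A constant risk would look like a late signal, and a falling risk could be hidden.

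Time at risk also varies between participants. Protocol 7.1.1 requires discontinuation for several reasons, and Protocol 5.5 and Appendix B allow for substantial early withdrawal. Participants whose lesions clear in the LTS period stop applying cream. Someone whose last application is at Week 20 has a TEAE window closing near Week 24 (20 + 30/7 = 24.3), yet stays in the LTS and Week 52 denominators as if followed throughout.

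The populations differ too. LTS-EV leaves out those who stopped during CT, and also anyone who entered LTS clear and never re-treated.

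This was a one-year safety study required after marketing approval (Protocol 2.2). What is at stake is whether its report can show how risk per unit time behaves with longer use.

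**Working it through.** **The plan's own figure.** Protocol 10.1 claims more than a 99% chance of seeing at least one event with 100 participants at an underlying rate of 5%. 1 − 0.95^100 = 0.994, so it reproduces. The calculation works only if that rate is a proportion of participants, which matters for one of the objections.

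**Inputs from the documents.** CT 8 weeks; LTS 44 weeks; TEAE window to 30 days after last application; about 100 participants.

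**Assumptions, not in the documents.** The CT percentage p (range shown), a hazard that is the same in both periods, and mean LTS follow-up.

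**Step 1, ratio of lengths.** 44/8 = 5.5. With the 30-day tail, (44 + 30/7)/8 = 48.3/8 = 6.0.

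**Step 2, LTS percentage with unchanged hazard.** p_LTS = 1 − (1 − p)^(t/8), where t is LTS follow-up in weeks. For example, 1 − 0.95^5.5 = 24.6%, and 24.6/5 = 4.9. The last two columns put the mean follow-up in place of t, as if everyone were followed for the mean.

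| CT % | LTS %, t = 44 | LTS/CT ratio, t = 44 | Ratio, t = 30 | Ratio, t = 22 |
|---|---|---|---|---|
| 1 | 5.4 | 5.4 | 3.7 | 2.7 |
| 5 | 24.6 | 4.9 | 3.5 | 2.6 |
| 10 | 44.0 | 4.4 | 3.3 | 2.5 |
| 20 | 70.7 | 3.5 | 2.8 | 2.3 |
| 30 | 85.9 | 2.9 | 2.5 | 2.1 |
| 50 | 97.8 | 2.0 | 1.9 | 1.7 |

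With the 30-day tail added to 44 weeks, the ratio is 5.9 at CT 1%, 5.3 at 5% and 2.0 at 50%.

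**Step 3, the converse.** Equal crude percentages in the two periods mean equal cumulative hazards, so with full follow-up the LTS hazard would be 8/44 = 18% of the CT hazard.

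**Step 4, the one-year figure.** With full follow-up, CT 5% leads to 1 − 0.95^(52/8) = 28.3% at 52 weeks. If mean LTS follow-up is 30 weeks, observed time is 38 weeks and the crude figure is 1 − 0.95^(38/8) = 21.6%. The hazard is the same; only the observed time has changed.

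**Step 5, the exposure-adjusted rate.** First events per 100 person-years = 100 × 52.18 × [−ln(1 − p)/8]. This gives 6.6 for CT 1%, 33.5 for CT 5% and 145.5 for CT 20%. The matching LTS percentages (5.4%, 24.6%, 70.7%) give the same rates, as they should.

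**Step 6, precision.** With 100 participants, no dropout and no censoring at first event, CT supplies 100 × 8/52.18 = 15.3 person-years and LTS 100 × 44/52.18 = 84.3. One event in LTS is 100/84.3 = 1.2 per 100 person-years. The exact Poisson limits for one event are 0.025 (from 1 − e^(−m) = 0.025) and 5.57 (from e^(−m)(1 + m) = 0.025). Divided by 84.3, the interval is 0.03 to 6.6 per 100 person-years.

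**The case against.** The strongest reply is that the plan does what it set out to do. The aim is to describe types and frequencies of TEAEs, no hypothesis is tested, and neither document plans a CT-versus-LTS contrast. This stands in part. A reader might infer that adverse events are reported only for two unequal periods and that the long-term question is left unanswered. The documents do not support that: the Baseline to Week 52 tables in the FAS give one-year crude incidence, exposure and disposition are tabulated, and all events are listed.

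Other stronger readings also fail:

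- **A conflict with Protocol Table 12.** The table names its summary metric a rate of TEAEs, which might suggest that person-time was promised. It states no time denominator, and Protocol 10.1 uses rate for a proportion. Number and percentage is consistent with that use.
- **LTS figures must come out several times higher.** The size depends on event frequency, follow-up and a constant hazard. For a category already common in CT, such as any TEAE might be, the ratio is about 2 or less. A constant hazard is also doubtful, since CT treats all baseline lesions continuously and LTS treats only active ones.
- **Every adverse event table is certain to be crude.** Appendix A gives titles only, and the table shells are in a separate document. What can be said is that SAP 9.2.2 specifies percentages and nothing in the SAP announces person-time.
- **The CT rate restricted to LTS-EV would be a clean comparator.** It would not. It selects on later behaviour, removing CT discontinuers and their events, and anyone who never re-treated.

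One further caution stands: calendar person-time in LTS mixes treated and untreated days, so a lower LTS rate could reflect less exposure rather than falling risk.

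**Conclusion.** The point holds as an inexpensive improvement to the reporting; it is not an error that invalidates the primary summary. The crude CT and LTS percentages cannot be compared. Under a constant hazard and full follow-up, length alone would raise the LTS figure about 5-fold for uncommon events (the likely range for most adverse events of interest), 3.5-fold at CT 20% and 2-fold at CT 50%. With a mean LTS follow-up of 22 weeks, the range is 1.7 to 2.7. The one-year percentage answers the descriptive question, but it understates one-year risk to the extent that participants leave early or their TEAE windows close early. The documents give no dropout figure, so the size of that effect is unknown. What the planned tables cannot show is whether risk per unit time changes with longer use.

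**What to change.** Keep n (%). In SAP 9.2.2 and the matching Appendix A tables, add the number of participants with a first event per 100 person-years at risk, with 95% CI, for CT, LTS and the whole study. Cover at least adverse events of interest, ASRs, and serious, treatment-related and Grade 3 or higher TEAEs.

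Define time at risk in the SAP:

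- Censor at first event or at the end of the participant's TEAE window. The duration in SAP 6.4 does not serve as it stands: it stops at the last application, while the events counted run 30 days further, and it starts at Day 1, so LTS needs its own start date.
- State whether no-treatment cycles count as time at risk. If they do, say so in a table footnote.

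If a CT rate restricted to LTS-EV is shown, label it as conditional on entering LTS and re-treating. A footnote on the n (%) tables should say that CT and LTS percentages cover different lengths of time and different populations.

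The event, last-application and treatment-cycle dates are already collected, so no visit or data item is added. The cost is SAP wording, a few columns and some programming. Intervals for rare events will be wide, which reflects what about 100 participants can show.
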